Preliminary analyses. HLM assumes multivariate normality of residuals at both within site: level-1 and between sites: level-2. During data cleaning, the univariate distribution of each variable will be examined using boxplots or stem-and-leaf displays to check for excessive skewness and outliers¹¹⁶. Tests of normality will be conducted for all interval-level variables using the Kolmogorov-Smirnov Z-test. Investigators will employ appropriate power transformations (e.g., natural log or square root) when needed to normalize distributions.

Missing data. While a distinct advantage of HLM is the ability to incorporate data missing at random in the outcome variables, it assumes complete data for the predictor variables. Investigators expect to have two levels of missing data. First, some items on survey questionnaires are likely to be missing although investigators will attempt to minimize this possibility. For this type of item missingness, investigators will substitute the respondent's average of all completed items. Second, investigators expect to have wave missingness, where scores are missing due to participant attrition or to not attending some learning circles. For these cases, investigators will use multiple imputation methods as implemented in STATA and in the HLM8 computer program.

Taxonomy of models. For each outcome (knowledge, attitudes and behaviors), investigators will estimate the following series of models to test the hypotheses concerning change over time. *Baseline models.* The first step in any growth analysis is to select an appropriate functional form to represent individual change over time. Given the number of waves (6 max: pre, post after each of 4 sessions and follow-up) and the short time frame (~9 months), investigators will test whether change is linear or curvilinear over time. *Main effects of predictor variables.* Investigators enter the predictors in sets to test investigators' conceptual models. Omnibus hypothesis tests will be used to assess the importance of each set in explaining variance in the outcomes, net of the other variables in the model. Variables in the three domains will be investigated to assess their impact. Investigators will test the impact of each set of variables within each domain.

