As a reference point, investigators will first report the analyses from the pilot data collection for each of the primary outcome scales of the PC CARES measure related to the primary and secondary suicide prevention intervention. These 4 outcome scales are: suicidal prevention *knowledge, skills* related to handling suicidal behavior, *community of practice* to respond to suicide risk and suicidal behavior, and *intention to act* regarding suicide prevention. In the pilot data collection, only 2 assessments were collected for most participants: pre-intervention and follow-up. In order to provide a sense of the magnitude of the intervention effects, paired samples *t* tests were conducted to estimate within-person change as a difference score in these outcomes pre- to post-intervention. Results showed statistically significant increases of moderate effect size in three of the four primary outcome measures. This difference can be converted to an effect size (Morris & DeShon, 2002), which account for the correlation between the two scores. For the 82 participants with complete pilot data pre- and post- intervention: significant increases were found in the suicide prevention knowledge scale (increase from 3.27 (.77) to 3.84 (.61), ES: .69) (Morris & DeShon, 2002), the skills to handle risk and suicidal behavior scale (increase from 3.64(.80) to 4.05(.68), ES= .49), and the community of practice in response to suicidality scale (increase from 3.52(.81) to 3.90(.78), ES= .43). The increase in the intention to act subscale was not statistically significant and much smaller in effect (increase from 3.84(.59) to 3.91(.60), ES = .12). Investigators believe that the within-person changes to the 'intention to act' is not significantly higher in PC CARES participants because those who voluntarily participate in the intervention are already highly motivated to take prevention action. Indeed, by attending the PC CARES intervention, they are taking action for prevention in their home communities. The ceiling effect is expected.

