In a paper that will be submitted shortly, investigators describe this process formally and apply it to the pilot study of the PC CARES intervention. In that analysis they found that PC CARES had its largest impact via the social effects of prevention and the diffusion of behavior change. Across all 39 items on the behavioral survey, 26 (66.7%) items showed significant positive change in the close associates of participants; a much higher level of change than in the participants themselves. The reason for this is typical of many community interventions. Where community-based, participatory research in tribal communities calls for open enrollment and participation, many of those who attend the intervention are members of that small community minority that are already engaged in the sorts of prevention behaviors and activities suggested by the intervention. In their case, looking for behavior change as a measure of intervention success among those who attend the training is likely to be limited. These self-selected participants tend to be highly motivated and there are therefore ceiling effects. Where investigators expect to see the biggest change is actually in the behavior of those who did not attend the intervention, but who are socially “close to” someone who did. In this case, measuring the *social efficacy* is more indicative of the overall impact of the community intervention than is the *individual efficacy*. In the pilot work, investigators were able to show that the PC CARES induced positive change most effectively in people close to PC CARES participants in terms of increasing their health promotion behavior and inducing positive behavior changes relating to prevention (#’s 2 and 4 below).

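### The SAP names normal residuals as the model assumption but tests, and may transform, the raw variables, and plans no residual check

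*SAP*

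**What the plan says.** The SAP's paragraph on preliminary analyses under Aim 1 opens with the assumption: "HLM assumes multivariate normality of residuals at both within site: level-1 and between sites: level-2". The steps that follow concern the variables themselves. During data cleaning, "the univariate distribution of each variable will be examined using boxplots or stem-and-leaf displays to check for excessive skewness and outliers". Next, "Tests of normality will be conducted for all interval-level variables using the Kolmogorov-Smirnov Z-test". The remedy is: "Investigators will employ appropriate power transformations (e.g., natural log or square root) when needed to normalize distributions".

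The paragraph does not describe any inspection of residuals. It gives no rule for choosing a transformation, does not mention reflecting a score first, and does not say whether a transformation used in one cohort would be used in the others.

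Three other parts of the SAP bear on this:

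- **Ceilings.** On the intention-to-act scale, Section C says: "The ceiling effect is expected". On behaviour change among attendees, Section D says: "These self-selected participants tend to be highly motivated and there are therefore ceiling effects". Neither statement covers knowledge, skills or community of practice.
- **Cohorts.** Sections A and C analyse each cohort of 150 separately, treat the staggered starts as repeats of the intervention, and compare findings across cohorts descriptively.
- **Model.** Section C writes the growth model with the outcome untransformed.

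The Data Analysis section of the 2023 combined protocol keeps the growth model but is silent on normality checks and transformations.

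**The concern.** The stated assumption and the planned check do not match. A test on a raw variable can fail when the model is sound, and can pass when the residuals at one level are badly behaved. The plan could therefore rescale an outcome or a predictor without cause, and could miss the problem it set out to find.

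The study has no comparison group, so it relies partly on similar change appearing in three cohorts. If a transformation is decided from the data, and cohorts are analysed one at a time, one cohort's slope could be in log units and another's in raw units. Those slopes cannot be compared directly. Where scores do sit at a ceiling, the two transformations named as examples would also push the distribution further from normal.

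**Working it through.** **1. Where normality is assumed.** Combining the two levels of the model in SAP Section C gives

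Outcome = γ00 + γ10·Time + u0 + u1·Time + r.

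The assumption concerns r (level 1) and u0, u1 (level 2). A raw outcome pooled over waves is a mixture whenever the mean or spread changes with time. In the pilot, knowledge went from mean 3.27 (SD .77) to 3.84 (SD .61), so the pooled scores mix two different distributions even if each is normal. Adding role or dosage effects mixes further. The model conditions on its predictors and gives them no distribution. Dosage takes four values (SAP, Key factors affecting participant outcomes), so it cannot be normal, yet it could fall under the interval-level variables to be tested.

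**2. What a change of scale does to a slope.** Take the pilot knowledge change and evaluate it at the means:

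- raw: 3.84 − 3.27 = 0.57
- square root: √3.84 − √3.27 = 1.960 − 1.808 = 0.15
- natural log: ln(3.84/3.27) = ln(1.174) = 0.16

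The same change reads as 0.57, 0.15 or 0.16 depending on the scale.

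**3. Direction of skew.** The documents report no skewness, no share of scores at the maximum and no pilot score range. The planned items are 7-point (SAP, Measures), and Section C says the pilot used the same measures. I therefore show two assumed ranges, 1-5 and 1-7. For maximum K, mean m and SD s, a scaled beta distribution was matched to the pilot figures:

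μ = (m−1)/(K−1); v = [s/(K−1)]²; c = μ(1−μ)/v − 1; a = μc; b = (1−μ)c; skew = 2(b−a)√(a+b+1) / [(a+b+2)√(ab)].

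The pilot figures for intention to act are: "increase from 3.84(.59) to 3.91(.60), ES = .12". At baseline with K = 5: μ = 2.84/4 = 0.71, v = (.59/4)² = 0.02176, c = 0.2059/0.02176 − 1 = 8.46, a = 6.01, b = 2.45, so skew = −0.54. Skew after transformation comes from 1,000,000 draws per row.

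| Scale, time | Assumed range | SDs below maximum, (K−m)/s | Raw | Square root | Log |
|---|---|---|---|---|---|
| Intention, pre | 1-5 | 1.97 | −0.54 | −0.76 | −1.00 |
| Intention, follow-up | 1-5 | 1.82 | −0.62 | −0.84 | −1.10 |
| Intention, pre | 1-7 | 5.36 | +0.04 | −0.17 | −0.39 |
| Intention, follow-up | 1-7 | 5.15 | +0.02 | −0.19 | −0.41 |
| Knowledge, follow-up | 1-5 | 1.90 | −0.56 | −0.78 | −1.04 |
| Knowledge, follow-up | 1-7 | 5.18 | +0.04 | −0.18 | −0.41 |
| Skills, follow-up | 1-5 | 1.40 | −0.84 | −1.08 | −1.38 |
| Skills, follow-up | 1-7 | 4.34 | −0.01 | −0.24 | −0.49 |
| Community of practice, follow-up | 1-5 | 1.41 | −0.74 | −1.00 | −1.31 |
| Community of practice, follow-up | 1-7 | 3.97 | +0.03 | −0.23 | −0.52 |

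The raw skew also depends on the assumed shape. A normal score censored at 5 gives intention a raw skew of −0.15 (pre) and −0.21 (follow-up), which the log takes to −0.63 and −0.67. Reflecting first, log(K+1−x) with K = 5, brings the beta-based intention skew to −0.05 and +0.02.

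So if left skew exists, the two named transformations increase it. Whether it exists depends on a range the documents do not give. There is no planned figure to reproduce, because no sample size or power calculation uses this step.

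**The case against.** The best defence is that the plan commits to little. It speaks of appropriate transformations when needed, and log and square root are only examples. A square, or reflection before the log, would also qualify. The Kolmogorov-Smirnov test is not the sole trigger either, because plots for skewness and outliers are read as well. All of this stands. The problem is a check on the wrong quantity followed by an unspecified choice, not a commitment to a harmful transformation.

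A reader might infer more in four respects, and the documents do not support it:

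- **That the outcome scores are left-skewed in general.** Ceilings are stated only for intention to act and attendees' behaviour. Pilot scale means of 3.27 to 4.05 sit near the middle of a 1-7 range. Rising pilot scores are reported as gains, so high was favourable there, but the planned numeric coding is not given. If full agreement were coded low, a log or square root would reduce the skew.
- **That unequal sample size would make the test flag one cohort and not another.** All three cohorts are planned at 150. Chance or real differences in distribution could separate them; planned size would not.
- **That a transformation would upset the linear-versus-curvilinear choice.** Nothing in the documents shows a material effect, and this point does not rest on one.
- **That a planned effect loses its units.** The .08 per session belongs to the original power calculation, which Section C re-did from pilot data.

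The cross-cohort comparison is descriptive, not a formal test of equal slopes. That limits the harm from mixed scales but does not remove it.

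**Conclusion.** The point holds and is minor. The SAP states the right assumption, aims its check and remedy at raw outcomes and possibly predictors, and plans no residual check at either level. That rests on the text alone. Two consequences are conditional. Cohorts would be on different scales only if a transformation were chosen cohort by cohort, which the plan neither requires nor rules out. Worse left skew would follow only if scores pile up at the maximum, high scores are favourable, and an unreflected log or square root is used. For intention to act on an assumed 1-5 range, the matched beta gives a shift from about −0.5 or −0.6 raw to −1.0 or −1.1 after a log. On an assumed 1-7 range there is no left skew to worsen.

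**What to change.** Amend the SAP paragraph on preliminary analyses as follows:

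- Replace the Kolmogorov-Smirnov screen of raw variables with residual plots at both levels of the Section C model: r at level 1, and the person effects u0 and u1 at level 2. The paragraph labels the levels as within and between sites, so the levels meant should be named.
- Do not transform predictors to make them normal.
- Analyse each outcome in its original units in all three cohorts.
- If residuals are clearly non-normal, use robust (sandwich) or bootstrap standard errors.
- Keep any transformed-outcome model as a sensitivity analysis, with the same transformation in every cohort.
- State the range and direction of each scale score, so that a ceiling can be recognised.

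The cost is SAP wording and slightly more diagnostic work, with no new data. Robust standard errors may be somewhat wider.

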understanding of) the research; and a 3 indicates that research evidence was interpreted inaccurately, leading to conclusions inconsistent with its intent. A narrative rationale is provided for each score. Investigators use both reviewers' ratings to calculate an average. In the pilot, with 35 LCs currently coded, there is a high level of accuracy, average of 1.21. Investigators consider scores under 1.5 to be adequate accuracy. If scores fall above this threshold, investigators will work with facilitators to improve their understanding of the research. *Fidelity.* Investigators assess fidelity for each of the 6 standard elements of each LC: (1) agreements/safe talk, (2) small wins, (3) the LC activity, (4) what we know, (5) what we think, and (6) what we want to do. Each dimension gets 0-1 for procedural components (i.e., presenting specific data, giving clear instructions to the group) that are present (1), absent (0), or not captured (NA) on the recording when the audio clearly misses some of the LC. Investigators will average these scores across two raters for each element, consider scores for each LC, and for each community, providing clues to decipher issues in a particular element, LC, or village, so it can be addressed. Pilot fidelity scores average .79 across two raters, indicating acceptable adherence to the curriculum.

(4) Measure PC CARES participants' knowledge, attitudes and behavior over time.

Participant recruitment: Based on the pilot study, investigators estimate 15-20 participants in each of 4 LCs and at least 50 distinct participants per village. The pilot study shows this is feasible with 376 participants attending LCs in 8 villages with less follow-up and support. With 3 villages per cohort, investigators estimate 150 people per cohort who attended at least 1 LC, with a total number of participants across 3 cohorts at 450. Investigators believe that those who are eligible to receive CEUs will be most likely to come to 3+ LCs and conservatively estimate a third will attend most LCs. For follow-up, investigators will invite all participants to complete the follow-up survey 3 months after the last LC. The research team will stop trying to contact participants after three attempts, and aim to have at least 25 (50%) of the follow-up surveys completed per village (Total=225). This level of recruitment was more than achieved in the pilot (65%) by working with local facilitators to find individuals and send the surveys back to UMass.

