Key factors affecting participant outcomes. Investigators expect particular factors, namely: (1) intervention participation on a community level (# sectors represented by participation in learning circles within each community), (2) participation on an individual level (dosage), and (3) participants' social role to influence changes in participant outcomes over time. These predictors are defined as follows: (1) *Cross-sector community participation* can be understood as a proxy for community capacity to collaborate for suicide prevention. Investigators found in the pilot research that if key stakeholders are able and willing to come together on a regular basis to learn about and make plans for how to prevent suicide, the community readiness for action is greater than in communities where this cross-sector participation does not occur. The attendance sheets will document sector participation using the 12 network positions described in SA2. For example, if LC1 in Village A has representatives from the school (+1), healthcare (+1), law enforcement (+1), and parents (+1) the cross-sector score for that LC = 4. Cross-sector participation for each community will be the average number of sectors in attendance over the 4 LCs. In the pilot work, these scores range from 2 to 8, and can be seen as a proxy for cohesion within village relationships and collaborative potential. These scores are also likely to vary across villages. (2.) *Individual participation:* Dosage: participants' attendance over time (1 to 4 LCs). (3) *Participant social role* will have two levels of categorization: "formal" meaning they are employed within the existing service ecology or "informal" in which they attend sessions based primarily on their social role as family member or friend. People will select one, primary role prompting their attendance. The specific subcategories under the "formal" or "informal" reflect the 12 *network positions* described in SA 2. Investigators hypothesize that social roles will shape one's level of change based on their previous suicide prevention training or lack of it. Investigators expect those without any training will gain the most knowledge, change of attitudes and prevention behavior.

Analytic Strategy. The broad goals of this aim describe trajectories of change over the 6-9 month course of the PC CARES intervention and identify predictors of differences in change.

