Power. In repeated-measures studies, both the number of waves of data per individual (e.g. level-1 units) and the number of persons (i.e., level-2 units) affect the power to detect various effects. In cases where the within person variance is large relative to the between-person variance of the growth rate and persons vary in their growth rates, the total sample size is less important in determining power than either the

frequency of the observations or the duration of the study. Using a formula provided by Raudenbush and Bryk (2001), investigators calculate that, given 6 time points spaced over 9 months, a sample size of a minimum 135 will be large enough to detect moderate effects in change rates. Using Optimal Design, a program used for multilevel modeling, to get an unstandardized effect size of .035, investigators would need a conservative estimate of 135 repeated measures of participants in each condition to obtain .8 power to detect between person differences. The effect size is based on the difference in slopes (change rate) between differences (e.g., people with high versus low dose; level of cross-sector collaboration; formal or informal social role). The total sample is 450 participants (50 participants per villages, 9 villages), and a conservative estimate of 135 participants with high dosage (3+ LCs), half the villages with 3+ sectors attending, and a third of the participants in formal roles.

Aim 2: Document the community-level impact of PC CARES by tracking the number and type of interactions aimed at preventing youth suicide and promoting wellness in participating villages, and describe changes in the supportive social networks of young people before and after the intervention.

Overview. Investigators will record the effectiveness of the intervention at the network and community level by performing pre- and post-intervention network interviews documenting the level and type of institutional/role interactions that take place across those institutions and the social positions best able to meet the needs of young people at risk for suicide. Ideally, these communities could be sorted into case and control groups.

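### Multiple imputation is prescribed for surveys after circles people did not attend, with no imputation model stated; the likelihood growth model needs no such step, and omitting dose from the imputation would attenuate the dose effect

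*SAP*

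**What the plan says.** The Missing data paragraph of SAP Aim 1 first notes that "a distinct advantage of HLM is the ability to incorporate data missing at random in the outcome variables". It then defines wave missingness as cases "where scores are missing due to participant attrition or to not attending some learning circles" and rules: "For these cases, investigators will use multiple imputation methods as implemented in STATA and in the HLM8 computer program". It does not say which variables enter the imputation model, how many imputations are made, or whether dose, dose-by-time or village is kept.

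Dose is one of three hypothesised predictors of change. Under Key factors affecting participant outcomes it is a person's "attendance over time (1 to 4 LCs"). A post-survey is given after each circle, so someone who misses a circle has no post-survey for it.

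The expected attendance is under Participant recruitment: "Based on the pilot study, investigators estimate 15-20 participants in each of 4 LCs and at least 50 distinct participants per village". The same paragraph aims for 50% follow-up completion and reports 65% in the pilot.

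Section C of the SAP, which updates the power analysis by cohort, assumes 30% missing data. The Data Analysis section of the 2023 combined protocol and SAP restates the growth model with five circles and seven occasions but gives no missing-data method. The 2018 paragraph is therefore the only rule.

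**The concern.** A survey lost to attrition was due and not returned. A survey for a circle the person did not attend was never due. The rule handles both in the same way, and the second kind is tied directly to a predictor under test: the lower the dose, the more post-circle scores are absent.

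An imputation model without dose fills low-dose people's empty waves from a pattern shared with high-dose people. That pulls the two groups' trajectories together and the dose-by-time coefficient towards zero. An imputation model with dose avoids this, but then supplies nothing that the likelihood model lacks when both use the same variables. The stated rule permits either implementation.

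**Working it through.** **The plan's own dose figure.** The Power paragraph relies on "a conservative estimate of 135 participants with high dosage (3+ LCs"). The Data Collection paragraph expects at least 15 people per village with four or more surveys; 15 × 9 villages = 135, and 135/450 = 30%. The figure reproduces. Participant recruitment says instead that investigators "conservatively estimate a third will attend most LCs", which would be 450/3 = 150.

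**Unattended post-circle cells, per village of 50.**
- Cells: 50 × 4 = 200.
- Attended: 4 × 15 = 60 to 4 × 20 = 80.
- Unattended: 140/200 = 70% to 120/200 = 60%.

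**Check against the 135.** Everyone counted attends at least one circle.
- With 30% at three or more circles, mean attendance is at least 0.7 × 1 + 0.3 × 3 = 1.6, so at most 1 − 1.6/4 = 60% is unattended.
- With one third, the mean is at least 2/3 + 3 × 1/3 = 1.67, so at most 58%.
- At 15 per circle there are 60 − 50 = 10 attendances beyond the first. A three-circle person uses two, so at most 5 per village, or 45 in nine villages, could reach three circles.

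The 70% end cannot coexist with 135 high-dose people. About 60% fits both statements.

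**Six-wave grid.** Assume that all 50 complete the pre-survey and every attender completes the post-survey. There are 300 cells. At 20 per circle and 50% follow-up, 50 + 80 + 25 = 155 are filled, so 145/300 = 48% are empty. At 65% follow-up, 50 + 80 + 32.5 = 162.5 are filled, so 46% are empty. Section C assumed 30%.

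**Effect on the dose coefficient, by simulation.** The true effect is 0.15 per circle on change over the whole period. There are six waves (months 0-4 and 7), with a random intercept and slope per person scaled to the pilot knowledge SDs (.77 and .61) and residual variance .1-.2. Missingness depends only on dose, except where follow-up is set by the stated completion rate. Imputation is multivariate normal with 10 imputations, and each scenario has 100 replicates. Entries are the percentage of the true dose-by-time effect recovered.

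| Scenario (N=450 unless stated) | ML, observed waves | MI with dose | MI without dose, all waves |
|---|---|---|---|
| 60% unattended, follow-up 50% (base) | 100 | 104 | 56 |
| Same, doses more spread | 98 | 100 | 56 |
| 70% unattended, follow-up 50% | 96 | 97 | 54 |
| 60%, other covariances, residual variance .1 | 100 | 104 | 65 |
| 60%, follow-up 65% | 100 | 101 | 67 |
| 60%, follow-up complete | 99 | 100 | 93 |
| Base, N=150 | 93 | 92 | 50 |

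The Monte Carlo standard error of the last column is about 2-3 points at N=450 and 4 at N=150. Standard errors from MI with dose exceeded those from ML by 6-12% (base case .0519/.0475 = 1.09). Base-case rejection rates were 0.89 (ML), 0.82 (MI with dose) and 0.43 (MI without dose).

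**Which cells cause the loss.** Smaller runs (50-60 replicates, 3 imputations) left missing follow-ups to the likelihood and imputed only the unattended circles, without dose. They recovered 82% (60% unattended, monthly circles), 74% (60%, equal spacing) and 84% (70%, monthly), a loss of 16-26%. With complete follow-up and equal spacing the loss was 14%. Imputing all waves in the smaller run of the base case recovered 52%, which agrees with the 56% above within simulation error.

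**The case against.** The strongest reply is that the SAP does not leave dose out of the imputation. Dose is a named predictor throughout Aim 1, a competent analyst would include it, and then there is no material bias. On that view the gap is one of detail. This stands as far as it goes: the attenuation is a risk from under-specification and does not follow from the rule as written.

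Two further points stand. The equivalence of imputation and likelihood holds only for the same variables under missing at random. The pre-survey's participant characteristics could serve as auxiliaries, although none is named for that purpose. The likelihood argument also does not cover the Wilcoxon and Friedman tests planned under Survey analysis. In addition, changing from imputation to ML is not protective in itself: a growth model without dose also infers low attenders' curves from other people's data. The protection comes from conditioning on dose.

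A reader might infer that the stated rule shrinks the dose effect by a third, or that imputing unattended circles alone does so. The documents support neither. A loss of a third or more at N=450 appeared only when dose was omitted and missing follow-ups were imputed as well. Nor should 70% be read as the expected share of unattended cells, given the 135 high-dose participants.

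**Conclusion.** The point holds as a choice of method that should be changed. The rule imputes scores for surveys that were never due, in an amount tied to the predictor under test and with no stated imputation model. One permitted implementation gives the likelihood answer with standard errors about 6-12% larger. Another attenuates the dose effect, by about 7-26% when follow-up is complete or left to the likelihood and by about 33-46% when missing follow-ups are imputed too.

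The cell shares (about 60% of post-circle cells, about 48% of the grid) follow from the plan's figures, given complete pre-surveys and full survey return by attenders. The attenuation figures rest on assumptions that are not in the documents: the true effect, the variances and covariances, and the missingness mechanism. They are for 450 pooled, whereas Sections A and C commit to each cohort of 150. There the single scenario run recovered 50% without dose, with ML itself at 93%. Section C confines moderator tests to knowledge and skills, so those are the outcomes exposed. The counts are for four circles; the five-circle design in the 2023 document was not computed.

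**What to change.** Amend the Missing data paragraph as follows:

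- **Primary analysis:** fit the growth model by ML/REML to the observed surveys at their actual times, with dose and dose-by-time in the model. Do not impute surveys for circles a person did not attend.
- **Any imputation:** limit it to surveys that were due but not returned, or to a sensitivity analysis. State the imputation model (dose, social role, village and their interactions with time) and the number of imputations.
- **Simple tests:** state which surveys the Wilcoxon and Friedman tests use.
- **Power:** reconcile the 30% missing-data assumption in Section C with the attendance and follow-up figures under Participant recruitment, and reconcile the 135 with the one-third statement.
- **Current design:** carry the rule into the 2023 Data Analysis section, which has five circles and no missing-data method.

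The analysis change costs SAP wording and reduces the work; the power reconciliation may need a rerun. No new data are needed. The drawback is that auxiliary information which imputation could have used is given up unless those variables are added to the growth model.
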